The 4 individual items used to evaluate pain intensity are 'worst', 'least', 'average', and 'now' (current pain). Pain ratings range from 0 to 10 for each item. The mean pain severity score will be calculated using the 4 individual items. This mean can be used if all 4 items are completed at a given assessment. If any individual item is not completed, the mean cannot be used. Descriptive statistics will be provided to summarize each individual item and the mean score at baseline, and each visit for the ITT population.

The 7 individual items used to evaluate pain interference include general activity, mood, walking ability, normal work, relations with other people, sleep, and enjoyment of life. Interference rating ranges from 0 to 10 for each item. BPI-SF pain interference will be scored as the mean of the 7 individual interference items. This mean can be used if more than 50%, or 4 of 7, of the total items have been completed at a given assessment.

BFI with 1st line AAT and 2nd line AAT

BFI will be performed in the screening period, at study visit at Week 1 (Day 1), Week 13, and every subsequent 12 weeks of 1st line AAT and 2nd line AAT, and at completion or discontinuation.

BFI is a simple questionnaire slip that consists of questions in 10 items to evaluate the malaise (subjective symptoms characterized as debility that includes physical and mental wasting) of cancer patients.

The mean of the 9items (except for the first Yes/No question) are used as a global BFI score.

When there are missing data, global BFI score can be acceptable as long as more than 50% of the 9 items (except for the first Yes/No question) were answered (e.g., a minimum of 5 of 9 items). The global BFI score is then calculated as the mean of answered questions.

ORR in best overall soft tissue response of RECIST guidelines with 1st line AAT

According to RECIST 1.1, the investigator or sub-investigator will evaluate the overall response in target, non-target, and new lesions in soft tissue at each time point. At the end of the 1st line AAT period, the best overall response will be assessed. Of subjects with measurable soft tissue lesion (at least 1 target lesion according to RECIST 1.1) in baseline imaging, the proportion of subjects with objective response (complete or partial response) will be evaluated.

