7 STATISTICAL METHODOLOGY

7.1 General Considerations

7.1.1 General Principles

For continuous variables, descriptive statistics will include the number of subjects (n), mean, standard deviation, median, minimum and maximum. When needed, the use of other percentiles (e.g.10%, 25%, 75% and 90%) will be mentioned in the relevant section. Frequencies and percentages will be displayed for categorical data. A missing category will be added to categorical variables where data is missing.

Summaries based on ITT (e.g. disposition, baseline and efficacy data) will be presented by planned treatment group, unless specifically stated otherwise. Safety analysis and other summaries based on SAF will be presented by actual treatment received.

All statistical comparisons will be made using two sided tests at the α =0.05 significance level unless specifically stated otherwise. All null hypotheses will be of no treatment difference, all alternative hypotheses will be two-sided, unless specifically stated otherwise.

All data processing, summarization, and analyses will be performed using SAS® Version 9.4 or higher on Windows. Specifications for table, figures, and data listing formats can be found in the TLF specifications for this study.

The Age (Derived) variable from EDC will be used for analysis. If date of birth is incomplete, the variable Age from EDC will be used for analysis.

Year will be calculated as (days/365.25) rounded up to 1 significant digit.

Month will be calculated as (days/30.4375) rounded up to 1 significant digit.

Time to event or duration of event endpoints will be based on the actual date rather than Visit Day.

For the definition of subgroups of interest please refer to section 7.8.

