7.4.3.7 Brief Fatigue Inventory (BFI) with 1st Line AAT and 2nd Line AAT

Descriptive statistics for global fatigue score and its change from baseline will be summarize by visit and treatment group for the ITT population. These measurement values and changes from baseline will be plotted as mean +/- SD plot.

Global fatigue score will be categorized according to the following categories by treatment group:

- Mild: global fatigue score be in range from 1 to 3.
- Moderate : global fatigue score be in range from 4 to 6.
- Severe : global fatigue score be in range from 7 to 10.

Counts and percentages of subjects in each of these categories will be summarized for each treatment group.

7.4.3.8 Objective Response Rate (ORR) in best Overall Soft Tissue Response of RECIST Guidelines with 1st Line AAT

For the comparison of ORR between the enzalutamide and flutamide groups, the stratified Cochran–Mantel–Haenszel test will be used. The stratification factor will be the disease stages (M0/N0, M0/N1, or M1) used as stratification factor for allocation.

ORR, its Clopper-Pearson exact confidence interval and its count within stratification will be summarized for each treatment. Mantel-Haenszel common risk difference for response (enzalutamide - /flutamide) and its 95% confidence interval based on the variance claimed by Sato (1989) will be estimated. And count and percentage of overall soft tissue response which is assessment using RECIST 1.1 will be tabulated. The summarized category is shown as follows:

- Complete response (CR)
- Partial response (PR)
- Progressive disease (PD)
- Stable disease (SD)
- Non-evaluable (NE)

Table 7-1: Definition of time to event and censor

	TTPP1	TTPP2	2nd TTPP	Time to PSA 50%/90% decline	TTF1	TTF2	rPFS	MFS
Subjects without PSA value at baseline or in observation period	Considered as censoring at randomization	Considered as censoring at randomization	Excluded from analysis	Considered as censoring at randomization	Not considered as censoring *To be judged based on continuation of study treatment	Not considered as censoring *To be judged based on continuation of study treatment	Not considered as censoring *To be judged based on result of radiographic assessment	Not considered as censoring *To be judged based on result of radiographic assessment

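### The BFI severity bands (1–3, 4–6, 7–10) leave gaps for a score that is a mean, so some valid scores fall in no category; the effect is confined to one descriptive, exploratory table.

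*SAP*

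**What the plan says.** The score is defined in the BFI paragraphs of SAP 6.1.4: "The mean of the 9items (except for the first Yes/No question) are used as a global BFI score". Missing items are allowed, since the "global BFI score can be acceptable as long as more than 50% of the 9 items" have been answered (the SAP's example is five of nine), and "The global BFI score is then calculated as the mean of answered questions".

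SAP 7.4.3.7 first summarises this score and its change from baseline as a continuous variable, by visit and treatment group, with plots of mean and SD. It then adds three categories. The lowest is given as "Mild: global fatigue score be in range from 1 to 3". The other two are a moderate band, 4 to 6, and a severe band, 7 to 10.

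The categories are used as follows: "Counts and percentages of subjects in each of these categories will be summarized for each treatment group".

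No category is given for a score below 1, and nothing is said about scores between bands. The protocol (7.4.3.5) plans only summary statistics for the BFI and has no bands.

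**The concern.** The bands are written for a whole-number score, but the score being banded is a mean. A subject who rates six items 3 and three items 4 has a sum of 6×3 + 3×4 = 30 and a mean of 30/9 = 3.33. That is a valid, complete score, and it is neither mild nor moderate. A subject with little or no fatigue, scoring below 1, also has no place in the table.

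Applied literally, the table has counts that can fall short of the number assessed and percentages that need not sum to 100%. Otherwise, whoever programs the table must decide where these scores go. In an open-label trial that choice is better fixed in the plan, particularly as the scores concerned include those at the boundaries between categories. Fatigue is also a result that readers will look for: Protocol 1.2.2.3 reports it as an adverse reaction in 25.3% of the enzalutamide group of the global chemotherapy-naive study.

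**Working it through.** The plan states no figure on this point to reproduce. The check is whether the bands cover every value that the score can take.

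**Inputs**
- Score = (sum of answered items) / (number answered), with 5 to 9 items answered (SAP 6.1.4).
- Bands, ends included: 1 to 3, 4 to 6, 7 to 10 (SAP 7.4.3.7).
- Item scale: not given for the BFI in the available text. Assumption: whole numbers from 0 to 10. The upper limit of the severe band points to a maximum of 10. The minimum is varied below.

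**Nine items answered, item minimum 0.** The sum runs from 0 to 90, giving 91 attainable means in steps of 1/9.

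| Range of mean | Sums | Number of values | Category in SAP |
|---|---|---|---|
| 0 to <1 | 0–8 | 9 | none |
| 1 to 3 | 9–27 | 19 | mild |
| between 3 and 4 | 28–35 | 8 | none |
| 4 to 6 | 36–54 | 19 | moderate |
| between 6 and 7 | 55–62 | 8 | none |
| 7 to 10 | 63–90 | 28 | severe |

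Classified: 19 + 19 + 28 = 66. Unclassified: 9 + 8 + 8 = 25, and 25/91 = 27%.

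**Nine items answered, item minimum 1.** Sums run from 9 to 90, giving 82 values. The gap below 1 disappears and the other two remain: 8 + 8 = 16, and 16/82 = 20%.

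**Some items missing, item minimum 0.** Unclassified values are 13/51 with five items answered, 16/61 with six, 19/71 with seven and 22/81 with eight, that is 25.5% to 27.2%.

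**Does another rule in the SAP close the gaps?**
- Rounding: SAP 7.1.1 gives rounding rules for years and months, for example "Month will be calculated as (days/30.4375) rounded up to 1 significant digit", and none for the BFI score.
- Missing category: SAP 7.1.1 adds one where data are missing. A score of 3.33 is observed, so that category does not apply.

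**Would rounding to the nearest whole number be enough?** With halves rounded up and item minimum 0, the nine-item sums divide into 0–4 (5 values, no category), 5–31 (27, mild), 32–58 (27, moderate) and 59–90 (32, severe). The two inner gaps close, but means from 0 to 4/9 still have no category.

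**The case against.** The strongest reply concerns consequence. The BFI is an exploratory endpoint with no planned test, and the continuous summaries in the same section use every valid score. Nothing in the SAP says that unclassified subjects are excluded, and a table whose counts fall short of the number assessed would probably be noticed during programming. All of this stands, and it is why the severity is low.

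A second reply is that the SAP refers to table specifications (7.1.1) and a data specification document (7.11) that are not available here, and a rounding rule could be in either. Whole-number bands would fit such a rule. This lowers certainty about what the final table will show. It does not repair the SAP text, and nearest-integer rounding alone would leave scores below 0.5 without a category if such scores can occur.

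A third reply is that the gap below 1 depends on an item minimum that the available text does not give. That is correct. The gaps between 3 and 4 and between 6 and 7 do not depend on it.

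A reader might also infer that a quarter or more of the subjects will be missing from the table. The documents do not support this, because they give no distribution of BFI scores. Under purely assumed gamma-shaped distributions with (mean, SD) of (1.5, 1.5), (2, 1.8) and (3, 2), placed on the 1/9 grid, about 53%, 43% and 29% of subjects would be unclassified. At the two lower means most of that is scores below 1: 46.7 and 33.6 percentage points, with 6.6 and 9.9 in the two inner gaps. At a mean of 3 the split is 11.2 and 17.6. These figures only show how far the share depends on the assumption.

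**Conclusion.** The concern holds in limited form. The banding rule in SAP 7.4.3.7 does not fit the score defined in SAP 6.1.4. This is an error in the rule as written, beyond a lack of detail. For whole-number items from 0 to 10, 25 of 91 attainable nine-item means (27%) have no category; with an item minimum of 1 the figure is 16 of 82 (20%). Both count attainable values, and the share of subjects affected cannot be derived from the documents.

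It would go too far to conclude that the trial's fatigue comparison is wrong. Only the severity table is affected. The continuous BFI summaries and plots, the primary analysis and the sample size do not depend on the bands. Label: wrong as written, low severity.

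**What to change.** Replace the three bands in SAP 7.4.3.7 with contiguous bands on the unrounded mean, keeping the SAP's own lower cut-points of 1, 4 and 7:

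- none/minimal: 0 to <1
- mild: 1 to <4
- moderate: 4 to <7
- severe: 7 to 10

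Under the 0–10 assumption these hold 9, 27, 27 and 28 of the attainable nine-item means, and 9 + 27 + 27 + 28 = 91, so every score is classified. With fewer items answered the bands still cover the whole range.

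Rounding to the nearest whole number plus a row for no fatigue would also give full coverage, but it is a different rule. It would place sums 5–8, 32–35 and 59–62 (12 of the 91 values) one category higher. Whichever convention is chosen should therefore be written down before the table is produced.

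The cost is one line of SAP text and a small change to the table program. No new data are needed. If the SAP is not reopened, the change can be stated and justified in the clinical study report, as SAP Section 1 provides.

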2.2 Study Design and Dose Rationale

2.2.1 Study Design

This is a randomized, open-label, comparative study on enzalutamide and flutamide.

Patients with M0 or M1 castration-resistant prostatic neoplasm that relapsed during CAB therapy with bicalutamide will be randomized to Group A or B. Dynamic allocation will be performed with minimization with biased coin technique. The following stages (M0/N0, M0/N1, or M1) will be used as allocation factors.

- M0/N0: No distant metastasis, and no lymph node metastasis
- M0/N1: Without distant metastasis, but with metastasis in lymph nodes distal to the aortic bifurcation
- M1: With distant metastasis (including metastasis in lymph nodes proximal to the aortic bifurcation)

For subjects in Group A, enzalutamide is administered as the 1st line AAT. After the confirmation of PSA progression, medication is changed from enzalutamide to flutamide as the 2nd line AAT. For subjects in Group B, flutamide is administered as the 1st line AAT. After the confirmation of PSA progression, medication is changed from flutamide to enzalutamide as the 2nd line AAT. The treatment period with each drug should not be more than 2 years from the enrollment of the last subjects.

PSA progression will be defined according to the consensus guidelines of PCWG2. For patients with PSA declines at Week 13, the PSA progression date is defined as the date that a $\geq 25\%$ increase and an absolute increase of ≥ 2 ng/mL above the nadir is documented, which is confirmed by a second consecutive value obtained 3 or more weeks later. For patients with no PSA decline at Week 13, the PSA progression date is defined as the date that a $\geq 25\%$ increase and an absolute increase of ≥ 2 ng/mL above the baseline is documented.

Data for the analysis of primary endpoint TTPP1 will be cut-off if not less than 135 events of PSA progression occurred in association with the 1st line AAT.

After the discontinuation of the 1st line AAT due to PSA progression or other reasons, the 2nd line AAT will be started. Subjects who discontinued the 1st line AAT due to PSA

progression will start the 2nd line AAT within 6 weeks after the date of examination that identified PSA progression. Subjects who discontinued the 1st line AAT due to other reasons will start the 2nd line AAT within 6 weeks from the day when the investigator or sub-investigator decided the discontinuation.

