3.4 Criteria to Shift from 1st Line AAT to 2nd Line AAT

If any of the following is satisfied, the study drug will be shifted to the 2nd line AAT after the discontinuation of the 1st line AAT:

- 1. PSA progression
- 2. In case where the 1st line AAT is to be discontinued due to AEs, but the investigator or sub-investigator considers that there is no problem in the subject tolerance to transition to the 2nd line AAT
- 3. In case where the 1st line AAT is to be discontinued due to progression of disease other than PSA progression, but the investigator or sub-investigator considers that there is no problem in the subject tolerance to transition to the 2nd line AAT.

In any of the following cases, study treatment will be discontinued without shifting to the 2nd line AAT:

1. In case of enzalutamide as 2nd line AAT, subjects with seizure as an AE

- 2. In case of flutamide as 2nd line AAT, subjects with the latest AST or ALT exceeding the upper limit of normal
- 3. Other cases that the investigator or sub-investigator considers unsuitable for study continuation

4 **TREATMENT(S)**

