6.1.2 Secondary Efficacy Endpoints

Time to PSA progression with 1st line AAT + 2nd line AAT (TTPP2)

Time to PSA progression with 2nd line AAT is defined as the period from Day 1 of 2nd line AAT to the date of PSA progression with 2nd line AAT. TTPP2 will be the total of time to PSA progression with 1st line AAT and time to PSA progression with 2nd line AAT.

PSA response rate to 1st line AAT (decrease by at least 50% or 90% from baseline)

PSA response will be defined as PSA decreased by at least 50% or 90% from baseline when at least 3 weeks passed after the lowest PSA decreased by at least 50% or 90% from baseline in the 1st line AAT period after baseline. The proportion of the subjects who achieved PSA response will be evaluated.

PSA response rate to 1st line AAT at Week 13 (decrease by at least 50% or 90% from baseline)

PSA response will be defined as the lowest PSA at Week 13 decreased by at least 50% or 90% from baseline in the 1st line AAT period. The proportion of the subjects who achieved PSA response will be evaluated.

Time to PSA decrease by 50% from baseline with 1st line AAT

Time to PSA decrease by 50% with 1st line AAT is defined as the period from the date of randomization to the day when the decrease of PSA from baseline by 50% is first identified.

Time to treatment failure of 1st line AAT (TTF1)

Time to treatment failure is defined as the period to study drug discontinuation for any reason that includes disease progression, onset of AEs, subjects' request, or death. The following will be evaluated.

The period from randomization to discontinuation of 1st line AAT will be evaluated.

Time to treatment failure of 2nd line AAT (TTF2)

The period from randomization to discontinuation of 2nd line AAT will be evaluated.

rPFS

Imaging examination will be performed with chest CT, abdominopelvic CT or magnetic resonance imaging (MRI), and bone scintigraphy in the screening period, at study visit every 12 weeks after Week 1 (Day 1) of 1st line AAT irrespective of switching the drugs, and at

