Treatment line is defined as 1st line AAT and 2nd line AAT. When analysis by treatment line is provided, divided to data of 1st line AAT and 2nd line AAT, and calculate descriptive summarization or frequency etc.

7.2 **Study Population**

7.2.1 **Disposition of Subjects**

- Number of subjects with informed consent (overall only)
- Number of subjects randomized with discontinued before randomization (overall only)
- Number of subjects randomized, by treatment group and overall
- Number and percentage of subjects in each analysis set, by treatment group and overall
- Number and percentage of subjects in with transition to 2nd line AAT, by treatment group and overall
- Number and percentage of subjects who had discontinued study drug during 1st line AAT to end of 2nd line AAT, by treatment group and overall
- Number and percentage of subjects who had discontinued study drug by primary reason for treatment discontinuation during 1st line AAT to end of 2nd line AAT, by treatment group and overall
- Number and percentage of subjects who had discontinued study drug during 1st line AAT and not transition to 2nd line AAT, by treatment group and overall
- Number and percentage of subjects who had discontinued study drug by primary reason for treatment discontinuation during 1st line AAT, by treatment group and overall
- Number and percentage of subjects who had discontinued study drug by primary reason for treatment discontinuation during 2nd line AAT, by treatment group and overall
- Number and percentage of screening failure subjects for overall
- Number and percentage of subjects who participated in each study visit, by treatment group and overall for the ITT population

A listing of all randomized subjects discontinued from study treatment, by center and by treatment group, the specific reason for discontinuation, and the last dose day and date will be presented.

7.2.2 **Demographic and Other Baseline Characteristics**

Demographic and other baseline characteristics will be summarized by treatment group as randomized for all subjects in the ITT population. Additionally same summaries will be provided for subject in the SAF population.

Descriptive summary statistics will be presented for continuous variables of:

- Age
- Height
- Weight
- Body Mass Index (BMI)
- Baseline serum PSA value
- Baseline lactate dehydrogenase (LDH) value
- Baseline hemoglobin value
- Baseline alkaline phosphatase (ALP) value

- Baseline serum albumin
- Baseline creatinine value

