7.4.3 Analysis of Exploratory Endpoints

7.4.3.1 Time to PSA Progression with 2nd Line AAT (2nd TTPP)

2nd TTPP is defined as the period from the start of 2nd line AAT to the first day when PSA progression is objectively identified. Convention of censoring is specified in Table 7-1.

The 2nd TTPP will be assessed by the same method as that with the Time to Treatment Failure of 2nd Line AAT (TTF2).

7.4.3.2 PSA Response Rate to 2nd line AAT (Decrease by at Least 50% or 90% from Baseline)

The PSA response rate to 2nd line AAT decreasing by at least 50% (or by at least 90%) will be calculated by treatment groups of subjects with baseline PSA value and PSA measured at least once at least 3 weeks passed after the lowest PSA. The PSA response rate to 2nd line AAT will be assessed by the same method as that with the PSA response rate to 1st line AAT.

Water fall plot will be made to present the percent change of PSA from baseline at the lowest PSA value (except within 3 weeks from baseline) for patient who have at least one time point PSA reduction in the 2nd line AAT period, and the highest PSA value (except within 3 weeks from baseline) for patient who have never had PSA reduction, respectively.

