Death during the study	Subjects who died during treatment with the first study drug are considered as censoring at final PSA measurement before death	Considered as censoring at final PSA measurement before death	Subjects who died during treatment with the first study drug are excluded from analysis Subjects who died during treatment with the second study drug are considered as censoring at final PSA measurement before death	Considered as censoring at final PSA measurement before death	The event is considered to occur at the time of death	The event is considered to occur at the time of death	The event is considered to occur at the time of death	The event is considered to occur at the time of death
Subjects who discontinued treatment during the study	Subjects who discontinue the first study drug are considered as censoring at final PSA measurement before discontinuation	Considered as censoring at final PSA measurement before discontinuation	Subjects who discontinue the first study drug are excluded from analysis Subjects who discontinue the second study drug are considered as censoring at final PSA measurement before discontinuation	Considered as censoring at final PSA measurement before discontinuation	The event is considered to occur at the time of discontinuation	The event is considered to occur at the time of discontinuation	Considered as censoring at final radiographic assessment before discontinuation	Considered as censoring at final radiographic assessment before discontinuation

Subjects who used prohibited concomitant medication or therapy during the study	Subjects who use one with the first study drug are considered as censoring at final PSA measurement before use	Considered as censoring at final PSA measurement before use	Subjects who use one with the first study drug are excluded from analysis Subjects who use one with the second study drug are considered as censoring at final PSA measurement before use	Considered as censoring at final PSA measurement before use	Not considered as censoring *To be judged based on continuation of study treatment	Not considered as censoring *To be judged based on continuation of study treatment	Considered as censoring at final radiographic assessment before use	Considered as censoring at final radiographic assessment before use

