Subjects who miss PSA data at least twice consecutively at scheduled PSA measurement points	Considered as censoring at final PSA measurement before missing data occur	Considered as censoring at final PSA measurement before missing data occur	Subjects who continue the first study drug are excluded from analysis Subjects who have shifted to the second study drug are considered as censoring at final PSA measurement before missing data occur	Considered as censoring at final PSA measurement before missing data occur	Not considered as censoring *To be judged based on continuation of study treatment	Not considered as censoring *To be judged based on continuation of study treatment	Not considered as censoring *To be judged based on result of radiographic assessment	Not considered as censoring *To be judged based on result of radiographic assessment
Subjects who miss radiographic assessment at least twice consecutively at scheduled radiographic assessment points	Not considered as censoring *To be judged based on result of PSA measurement	Not considered as censoring *To be judged based on result of PSA measurement	Not considered as censoring *To be judged based on result of PSA measurement	Not considered as censoring *To be judged based on result of PSA measurement	Not considered as censoring *To be judged based on continuation of study treatment	Not considered as censoring *To be judged based on continuation of study treatment	Considered as censoring at final radiographic assessment before missing data occur	Considered as censoring at final radiographic assessment before missing data occur

Sponsor: Astellas Pharma Inc. SAP Version 1.00

ISN/Protocol 9785-MA-3051

7.4.4 **Analysis of Other Variables**

PSA measurement

Descriptive statistics for PSA measurement and its change from baseline will be summarized at by visit and treatment group. These measurement value and change from baseline will be plotted as mean +/- SD plot.

Swimmer's plot

Swimmer's plot will be made to present treatment flow and event occurrence for each patient. This plot will include time on and off of the 1st/2nd line AAT continuations as a bar chart, and the points at which drug related AEs (by CTCAE grades), PSA progression, radiographic progression, PSA response, and death.

7.5 **Analysis of Safety**

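### As worded, the 2nd TTPP column of SAP Table 7-1 drops subjects who start the second drug after stopping the first for a reason other than PSA progression, and can censor others before 2nd-line Day 1

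*SAP*

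**What the plan says.** SAP 7.4.3.1 starts the clock at the second drug: "2nd TTPP is defined as the period from the start of 2nd line AAT to the first day when PSA progression is objectively identified".

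The censoring rules are in SAP Table 7-1, which repeats the table in protocol 7.10. Two cells of the 2nd TTPP column matter here.

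- Row for subjects who discontinued treatment: "Subjects who discontinue the first study drug are excluded from analysis", followed by "Subjects who discontinue the second study drug are considered as censoring at final PSA measurement before discontinuation".
- Row for two or more consecutive missed PSA measurements: subjects still on the first drug are excluded, and "Subjects who have shifted to the second study drug are considered as censoring at final PSA measurement before missing data occur".

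On how subjects reach the second drug, protocol 2.2.1 says "After the discontinuation of the 1st line AAT due to PSA progression or other reasons, the 2nd line AAT will be started". Protocol 3.4 likewise has the subject "shifted to the 2nd line AAT after the discontinuation of the 1st line AAT". It lists three routes: PSA progression; an adverse event, if the investigator sees no tolerance problem; and progression other than by PSA, on the same condition.

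**The concern.** Every subject in 2nd line has, by design, discontinued the first drug. An exclusion of those who discontinue the first drug, with no further condition, therefore conflicts with an endpoint that exists only for subjects who went on to the second. The practical question is what happens to subjects who switch without PSA progression. They take the second drug and follow its PSA schedule, yet the cell points to leaving them out.

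At stake is who is in the 2nd TTPP set. If membership depends on why a subject left 1st line, the two 2nd-line curves describe patients selected on a post-randomisation event. If the wording stays open, the choice falls to whoever programs the table, in an open-label study.

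The missed-PSA cell raises a different problem. It sorts subjects by whether they have shifted, not by when the visits were missed, so a gap in 1st line can set the censoring date for an endpoint whose time zero comes later.

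**Working it through.** **The plan's own figure.** No number is given for 2nd TTPP. The nearest is the TTPP1 calculation (SAP 4), which reproduces:

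- HR = 6/10.5 = 0.571.
- Events = 4 × (1.960 + 1.282)² / (ln 0.571)² = 134.2, rounded up to 135.
- Event incidence 0.858 (enzalutamide) and 0.966 (flutamide), mean 0.9122. Then 135/(2 × 0.9122) = 73.99, rounded up to 74 per group.
- 74/0.75 = 98.7, so 99, against 100 enrolled per group.

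Only the 135 is used below.

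**What discontinuing the first drug covers.**

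1. SAP 6.1.2 defines treatment failure by "study drug discontinuation for any reason that includes disease progression". On that meaning the cell removes every 2nd-line subject and leaves 0 in both groups.
2. The second sentence of the cell, and the cut-off, death, prohibited-therapy and missed-PSA rows, give rules for subjects on the second drug. The literal reading contradicts the column, so some narrower meaning is needed.
3. Suppose PSA-progression switches do not count as discontinuing. Take a subject who stops the first drug for an adverse event, without PSA progression, and switches. In the TTPP1 column, the cut-off row covers only those continuing the first drug, and the death row only those who died on it. With no missed visits and no prohibited therapy, the discontinuation row is the only one that gives this subject a TTPP1 censoring date. Its phrase must therefore include this subject.
4. The same phrase, in the same row, is the 2nd TTPP exclusion. Read consistently, it drops this subject.
5. If instead the phrase means only subjects who never shift, 2nd TTPP is right but this subject has no TTPP1 censoring rule. One phrase cannot serve both cells.
6. The SAP can draw the distinction. Its disposition list (7.2.1) counts separately those who "discontinued study drug during 1st line AAT and not transition to 2nd line AAT". SAP 7.11.3 also expects 2nd-line starts for reasons other than PSA progression.

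**Size of the exclusion.** The documents give no switch rate. As an assumption, let 50% to 100% of the 135 planned TTPP1 events lead to a switch: 135 × 0.5 = 67.5, so 68, up to 135. As a second assumption, let other-reason switches be 10% to 20% of all 2nd-line starts. The number dropped is then 68 × 0.10/0.90 ≈ 8 up to 135 × 0.20/0.80 ≈ 34. This illustrates scale and is not an estimate.

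**The missed-PSA cell.** First-line PSA falls on Days 1, 85, 113 and every 28 days after. 2nd line starts within 42 days of the examination that identified PSA progression. The dates are assumed. Time = censoring day minus 2nd-line start day; adding one day by convention would not change the sign.

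| Last PSA before gap | Missed | 2nd line starts | 2nd TTPP (days) |
|---|---|---|---|
| Day 141 | Days 169, 197 | Day 225 | 141 − 225 = −84 |
| Day 141 | Days 169, 197 | Day 267 (225 + 42) | 141 − 267 = −126 |
| Day 1 | Days 85, 113 | Day 141 | 1 − 141 = −140 |
| Day 1 | Days 85, 113 | Day 183 (141 + 42) | 1 − 183 = −182 |

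The prohibited-therapy cell in the same column ties each occurrence to the first or the second drug. The missed-PSA cell does not.

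**The case against.** The best defence is that the intention is plain. The row concerns subjects who discontinued treatment during the study, and protocol 6.1 describes a discontinuation as permanent, premature cessation of study treatment. On that view the sentence removes people whose treatment ended on the first drug, and nobody who took the second is lost. This is probably what was meant, and it disposes of one tempting inference: that the 2nd TTPP analysis will be empty. The rest of the column does not support that.

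The defence does not settle the adverse-event and non-PSA switchers, because the TTPP1 cell needs the same words to include them.

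On negative times, the defence is that SAP 7.1.2 resets study day and baseline for 2nd line, and that the rule choosing the earliest censoring date is written only in the TTPP1 section. Both points are fair. The problem also needs two consecutive missed 1st-line visits followed by a switch. It is a gap in the rule, and the documents do not show that it will occur.

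Two further inferences should be resisted.

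- 2nd TTPP is not the only endpoint that isolates the second drug. The 2nd-line PSA response rate does so too, and SAP 7.4.3.2 does not exclude by reason for leaving 1st line.
- Correcting the cell does not make the 2nd-line groups comparable. Protocol 3.4 bars entry to 2nd-line flutamide when the latest AST or ALT is above the upper limit of normal, and to 2nd-line enzalutamide after a seizure. Protocol 6.1 has drug-specific stopping rules for both drugs. Selection by drug remains.

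**Conclusion.** The point stands as a wording error with a limited but real effect. Applied consistently across its row, the discontinuation cell drops from 2nd TTPP subjects who switched after an adverse event or non-PSA progression, which protocol 3.4 allows. The missed-PSA cell can produce a censoring date before time zero. How many subjects either affects is unknown; the 8 to 34 above rests wholly on assumed switch rates, and the negative times on assumed visit dates. 2nd TTPP is exploratory and summarised descriptively without a between-group test. The TTPP1 test, its significance level and the 135 events are untouched.

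**What to change.** In the 2nd TTPP column, replace the exclusion in the discontinuation row with: *subjects who stop the first study drug and do not start the second are excluded; all who start the second are included, whatever the reason for stopping the first.* In the missed-PSA row, apply the rule only to PSA visits on or after 2nd-line Day 1. Leave the exclusion for prohibited therapy used with the first drug as it is: it is explicit, and it cannot create a negative time.

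Make the change in both SAP Table 7-1 and the protocol 7.10 table, or record it in the SAP as a change from the protocol. If the database is already locked, state and justify in the clinical study report which reading was used, as SAP section 1 requires for changes to the planned analyses.

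No new data are needed. The cost is a slightly more heterogeneous 2nd-line set, and the disposition table of reasons for stopping 1st line helps describe that mix.
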